3.2. Objectives

3.2.1. Main objective:

The objective of the study is to determine the efficacy of reinforcing standard treatment with repeated infusions of plasma from people ex-convalescent of COVID-19 disease (already discharged and/or with negative COVID-19 test results), transfused to COVID-19 patients still hospitalized, both COVID-19 plant and HUSLL ICU ([and collaborating centres participating in the multicentre study](#)). Comparing it with the results obtained with the exclusive use of standard treatment, which is being used in patients infected with COVID-19. Therefore, to assess the immunological efficacy of the reinforcement of standard treatment vs standard therapy without reinforcement.

3.2.2 Secondary objectives:

Secondary objectives are related to evaluating not only efficacy at the clinical level, but also tolerance, safety and immunological aspects. Below is a list of the main secondary objectives:

- To assess the serological response to Coronavirus SARS-CoV-2 in patients with plasma transfusion and compare it with patients who have received treatment standard.
- Analyse the influence of the number of antibodies of the donor on the clinical evolution of the recipient.

-Analyse the efficacy of the experimental treatment that will reinforce the standard treatment, comparing it with the exclusive standard treatment at the level of the main clinical parameters during and after the treatment.

-To assess the safety of experimental reinforced treatment, comparing it with standard treatment during and after treatment.

-To assess the tolerance of experimental reinforced treatment, comparing it with standard treatment during and after treatment.

-Evaluate the feasibility of the experimental reinforced treatment.

-To assess the virological response of patients with plasma transfusion versus patients with standard treatments.

-Find if there is a certain patient profile where this therapy is most effective, either by age group, blood group, sex, or presence/absence of other pathologies.

-On the contrary, determine if there is a certain profile of patients (as in the previous case) in which the treatment is less effective.

-To know retrospectively the parameters of antigenemia and viral load of convalescent patients infected by COVID-19.

-Find possible weak points of experimental therapy that need to be studied to be improved in future studies.

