4.3.3. Primary and secondary variables

The variables that will be collected will be those related to the study of the efficacy, tolerance, safety and clinical effects of the treatment. Below is the list of encoded variables:

VARIABLE NAME	UNITS	CODING	VALUE
Diagnostic date			Date
Date of birth			Date
Age	years		Number
Presence of concomitant disease		0	Yes
		1	No
Concomitant disease species			Name

Sex		0	Man
		1	Woman
Weight	Kg		Number
Height	cm		Number
Body mass index	Kg/cm ²		Number
Physical examination		0	Normal
		1	Clinically insignificant abnormality
		2	Clinically significant abnormality
Physical scans specify			Number
Blood pressure	mmHG		Number
Heart rate	lpm		Number
Respiratory rate	rpm		Number
Temperature	°C		Number
Oxygen saturation	%O ₂		Number
ECOG		0	Asymptomatic. Fully active.
		1	Intense activity restriction. Capable of daily work.
		2	Ambulatory and capable of self-care. Unable to work. Lifted more than 50% of the time awake.
		3	Capable of some self-care. Bed-chair life more than 50% of the time awake.
		4	Total disability. Chair-bed 100% of the time awake.
		5	Dead.
Electrocardiogram		0	Normal
		1	Abnormal. Clinically not significant.
		2	Abnormal. Clinically significant.
Concomitant medication		0	No
		1	Yes
Chest X-ray			Assessment
Concomitant medication specifies			Name
ANALYTICAL PARAMETERS			
Haemoglobin	g/dl		Number
Haematocrit	%		Number

Leukocytes	x10 ⁹ /l		Number
Absolute lymphocytes	x10 ⁹ /l		Number
Absolute neutrophil count	x10 ⁹ /l		Number
Monocytes	x10 ⁹ /l		Number
Eosinophils	x10 ⁹ /l		Number
Basophils	x10 ⁹ /l		Number
Medium Corpuscular Volume	fL		Number
Platelets	x10 ⁹ /l		Number
Prothrombin time	s		Number
Activated Partial Thromboplastin Time (APTT)	s		Number
INR			Number
Fibrinogen	mg/dl		Number
D-dimer	mg/dl		Number
Glucose	mg/dl		Number
Creatinine	mg/dl		Number
Glomerular filtration (CKD-EPI)	ml/min		Number
Sodium	mEq/l		Number
Potassium	mEq/l		Number
Chlorine	mEq/l		Number
Calcium	mg/dl		Number
Urea	mg/dl		Number
Urate	mg/dl		Number
Albumin	mg/dl		Number
Total proteins	mg/dl		Number
Iron	µg/dl		Number
Ferritin	ng/ml		Number
Ferry	mg/dl		Number
transferrin saturation index	%		Number
Reactive protein C	mg/dl		Number
AST	U/L		Number
ALT	U/L		Number
GGT	U/L		Number

LDH	U/L		Number
FA	U/L		Number
CPK	U/L		Number
Troponin I			Number
Procalcitonin			Number
IL-1			Number
Blood pH arterial blood gas			Number
PO ₂	mmHg		Number
HIV Serology		0	Negative
		1	Positive
HVB Serology		0	Acute infection
		1	Chronic infection

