		2	Past infection
		3	Immunized
		4	Negative
CMV Serology		0	Negative
		1	Positive
Syphilis Serology		0	Negative
		1	Positive
INMHEMATOLOGIC STUDY			
ABO Blood Group		0	A
		1	B
		2	AB
		3	O
Rh		0	Present
		1	Absent
Irregular Blood Group antibodies		0	Negative
		1	Positive
DIAGNOSTIC/MICROBIOLOGICAL PROCEDURES			
Quantitative titration of SARS-COV2 antibodies (IgG/IgM)		UA/mL	Number
RT-PCR SARS-COV-2		0	Negative
		1	Positive

Time to RT-PCR negativization	Days		Number
CLINICAL CRITERIA			
Pleural effusion		0	Negative
		1	Positive
PSI score		1	Valuation not required
		2	<=70
		3	71 - 90
		4	91 - 130
		5	>130
WHO Progression Scale		0	Uninfected; no viral RNA detection.
		1	Asymptomatic; viral RNA detection
		2	Symptomatic. Independent
		3	Symptomatic. Need for assistance
		4	Hospitalized. Oxygen-free
		5	Hospitalized. Oxygen with mask or nasal tips
		6	Hospitalized. Oxygen by non-invasive ventilation (NIV) or high flow.
		7	Intubation or mechanical ventilation. PO2/FIO2>= 150; or SpO2/FO2> 200
		8	Mechanical ventilation (pO2/FIO2< 150, or SpO2/FIO2< 200), or vasopressor (norepinephrine >0.3 microg/Kg/min)
		9	Mechanical ventilation (pO2/FIO2< 150, or SpO2/FIO2< 200), or vasopressor (norepinephrine >0.3 microg/Kg/min) o dialysis o ECMO
% of patients requiring ICU admission			Number
15-day mortality rate			Number
Mortality rate at 30 days			Number
Days of hospitalization			Number
SECURITY CRITERIA			
Emerging adverse effects (ASD) \geq GIII		0	No
		1	Yes
Type TEAE SPECIFY			Name
Cumulative rate/incidence of ASD \geq GIII in experimental branch			Number

Cumulative rate/incidence of emerging adverse events (ASD) any grade in experimental branch			Number
Hospital discharge date			Date
Exitus		0	Yes
		1	No

Table 1. Variables that will be included in the database of the study.

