5. DATA ANALYSIS: STATISTICS

A descriptive analysis of all variables will be performed. With the categorical variables, the global percentages and frequencies will be estimated. Normality tests and graphs will be used to determine if the quantitative variables follow a normal distribution. Normal distribution variables shall be expressed as mean \pm standard deviation and those without normal distribution shall be expressed as median and interquartile range. To describe the significance and associations between variables after the intervention, parametric and non-parametric tests will be used as appropriate (the student's t test of paired samples or the Wilcoxon test for quantitative variables and the ANOVA test for paired samples or Friedman test for qualitative variables). The correlations will be examined by the correlation of Spearman or Pearson ranges and a multivariate analysis will be performed to assess the effect of other factors such as the confusion/interaction effect, as well as to assess the possible construction of predictive models. A p-value $< 0,05$ shall be considered an indicator of a significant difference. SPSS v.23 software will be used for data analysis.

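### No primary variable is named and p<0.05 is the only rule, without multiplicity control, so the efficacy conclusion can be chosen after the data are seen

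*Combined protocol and SAP*

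**What the plan says.** Section 3.2.1 sets the aim: "The objective of the study is to determine the efficacy of reinforcing standard treatment with repeated infusions of plasma". It closes by restating that aim as "to assess the immunological efficacy of the reinforcement of standard treatment vs standard therapy without reinforcement". It gives no variable, time point or effect measure.

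Section 4.3.3 carries a heading that announces primary and secondary variables. Its text says "The variables that will be collected will be those related to the study of the efficacy, tolerance, safety and clinical effects of the treatment" and then gives a single list, captioned "Table 1. Variables that will be included in the database of the study". The list mixes identifiers, baseline data, laboratory values, virology, a block headed "CLINICAL CRITERIA" and safety items. No row is marked primary or secondary.

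Section 5 plans a description of every variable. On testing it says: "To describe the significance and associations between variables after the intervention, parametric and non-parametric tests will be used as appropriate". The tests then named are for paired samples (t test, Wilcoxon, paired ANOVA, Friedman), followed by correlations and multivariate models. The only decision rule is that p below 0.05 "shall be considered an indicator of a significant difference". Section 5 gives no order of testing, no adjustment for multiple tests, no analysis time point and no list of between-arm comparisons.

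**The concern.** The trial sets out to answer whether plasma works, and the plan does not say which result will answer it. Antibody titre, viral clearance, the WHO progression scale, mortality or hospital days could each be put forward afterwards as the measure of efficacy. Any of them below 0.05 could be called significant under the one stated rule.

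Other parts of the plan add choices. Clinical response is assessed at four follow-up visits (section 4.3.1, Table 3). The secondary objectives look for patient profiles in which the therapy works better or worse (section 3.2.2). The final analysis is stratified by type of standard treatment (section 4.1). The trial is open-label (section 4.1) and no target sample size is fixed (section 4.2.10), so neither blinding nor a fixed end point to recruitment limits the choice. At stake is whether a reported efficacy finding carries a known error rate.

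**Working it through.** **Is there a figure to reproduce?** No. The documents state no sample size, power or family-wise error rate. The only numerical input is the 0.05 threshold in section 5. Its sidedness is not given, and two-sided testing is assumed here.

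**Counting Table 1 (section 4.3.3).** By hand count the table has 86 rows. Those that can change after baseline are:

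| Group | Number |
|---|---|
| Examination, vital signs, ECOG, ECG, chest X-ray | 9 |
| Laboratory values | 42 |
| Antibody titre, RT-PCR, time to negative RT-PCR | 3 |
| Clinical criteria | 7 |
| Grade III or higher adverse effects, death | 2 |
| Total | 63 |

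The efficacy-type variables are the 3 virology and antibody items plus the 7 clinical criteria (pleural effusion, PSI score, WHO scale, ICU admission, 15-day mortality, 30-day mortality, hospital days). That makes 10, or 11 if the separate death variable is counted.

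**Formula.** Suppose plasma has no effect on any variable and there are k independent between-arm tests, each at two-sided 0.05. The chance of at least one false positive in either direction is 1 − 0.95^k. The chance of at least one in favour of plasma is 1 − 0.975^k.

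| k | Either direction | In favour of plasma |
|---|---|---|
| 1 | 5.0% | 2.5% |
| 10 | 40.1% | 22.4% |
| 11 | 43.1% | 24.3% |
| 60 | 95.4% | 78.1% |
| 63 | 96.1% | 79.7% |

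**Allowing for correlation.** The documents give no correlations, so these are assumed. Equicorrelated normal test statistics were simulated with no true effect (100,000 runs per setting):

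| k | Assumed correlation | Either direction | In favour of plasma |
|---|---|---|---|
| 10 | 0.3 | 35.0% | 17.7% |
| 10 | 0.5 | 28.8% | 14.6% |
| 11 | 0.5 | 30.3% | 15.0% |
| 60 | 0.3 | 85.0% | 48.1% |
| 60 | 0.5 | 66.7% | 33.8% |
| 60 | 0.7 | 42.8% | 21.5% |

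**Repeat visits.** Testing 10 to 11 efficacy variables at all four visits gives 40 to 44 tests. Under independence that is 1 − 0.95^40 = 87% to 1 − 0.95^44 = 90%. This is only an upper bound, because repeated measurements correlate and some of these variables have a single value per patient. The documents do not allow the true increase from visits, profile searches and treatment strata to be fixed.

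**After the fix.** One named variable at one time point, tested between arms at two-sided 0.05, gives 5%, or 2.5% in favour of plasma.

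**The case against.** A reader might infer that section 5 applies the 0.05 rule to all 60 or so variables and that a false efficacy signal is therefore close to certain. The documents do not support this, for four reasons.

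- Section 5 attaches the whole list to description, not to testing, and does not say which variables are compared between arms. Table 1 is captioned as the content of the database. The rule is under-specified. It does not declare efficacy on any single positive result.
- Forty-two of the variables are laboratory values. A difference in sodium, or one favouring control, is not an efficacy signal.
- The 95% figure needs independent tests. Several variables are closely linked, such as haemoglobin with haematocrit, prothrombin time with INR, and 15-day with 30-day mortality.
- The tests named are for paired samples. The calculation above concerns between-arm tests, which section 5 does not name. Within-patient tests can turn positive through natural recovery, which is a separate problem that these figures do not cover.

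It is also fair to say that this is a phase I pilot with openly exploratory secondary aims, and exploratory studies often go without a formal primary variable.

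These arguments stand against near-certainty, but they do not remove the gap. Section 5 does not restrict testing to any subset either. A pilot that states its aim as determining efficacy and sets a significance threshold needs either a primary variable or an explicit exploratory label.

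**Conclusion.** The concern holds in a limited form. No primary variable is named, 0.05 is the only rule, and nothing elsewhere in the documents supplies a hierarchy, time point or multiplicity control. The main efficacy conclusion is left open to choice after the results are known.

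The most relevant size is that for the 10 to 11 efficacy-type variables tested once each: about 40-43% under independence, or about 29-30% at correlation 0.5. In favour of plasma the figures are about 22-24% and about 15%. Even 15% is six times the 2.5% of one pre-named test (0.15 / 0.025 = 6). About 95% applies only as an upper case for all 60 or so variables tested independently, falling to about 67-85% at correlations of 0.5 to 0.3.

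These figures assume no plasma effect, two-sided between-arm tests that each have exactly 5% error, and illustrative correlations. Visits, profile searches and strata would raise them by an amount that cannot be determined from the documents.

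**What to change.** In section 4.3.3, name one primary variable at one time point, chosen by the sponsor to match the main objective. One example is the WHO progression scale at day 14. Death would then have to be added as the worst level, because the scale printed in Table 1 stops at 9 without one. If the sponsor means the immunological part of the objective to lead, a different variable would be needed.

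In section 5, state a between-arm test for that variable by assigned group, since the tests now listed are for paired samples. Apply the 0.05 rule to that test only. Report every other variable as an estimate with a 95% confidence interval, labelled secondary or exploratory.

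The example uses data already planned for collection. The cost is a short written amendment by the approval route in section 6.1, and secondary variables can no longer be called significant.

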4.2.9. Adverse events

4.2.9.1. Monitoring and recording of adverse events.

An adverse event (AA) is any harmful, unintended, or unfavourable medical event that occurs or worsens in a patient over the course of a study. It may be a new concurrent disease, the worsening of a concomitant disease, an injury, or any concomitant deterioration of the patient's state of health, including its analytical results regardless of its cause. Any worsening (i.e., any adverse and clinically significant variation in the frequency or intensity of an ailment that was present prior to study treatment) should be considered an AA. The diagnosis or syndrome is recorded in the Data Collection Notebook (CRD).

The investigator must record all non-serious and severe AAs related to the study treatment that occur from the signing of the informed consent up to 30 days after the last dose of the investigational treatment. Severe AA (AAG) that occurs after the signing of the informed consent but before initiating treatment should also be recorded.

The assessment of the AA will include the following aspects:

- Gravity: An AAG is all AA that https://correu.ssib.es/owa/-_msocom_1 :

1. Deathrolls.
2. Threaten life (an AA that, in the opinion of the investigator, carries an immediate risk of death).
3. Hospitalization or prolongation of hospitalization is necessary (hospitalization is defined as a hospital admission, regardless of the length of stay). Scheduled hospitalization, for socio-sanitary reasons or, for this study, that derived from COVID-19, will not be considered an AAG.
4. Persistent or significant disability or disability (substantial impairment of the patient's ability to perform normal activities).
5. Give rise to a congenital anomaly or birth defect.
6. It is an important medical event.

-Severity: The severity/intensity of adverse events (AA) is classified based on the patient's symptoms according to the current version of the toxicity criteria common for adverse events (CTCAE, Version 5.0);

https://ctep.cancer.gov/protocoldevelopment/electronic_applications/docs/CTCAE_v5_Quick_Reference_5x7.pdf

- Causal relationship: The relationship will be defined as **suspicious** in a situation where there is a reasonable possibility that the administration of the investigational medicinal product caused the adverse event. When there is a remote or low probability that the event is related to the study drug then the relationship will be defined as non-suspicious.

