4.2.10. Sample size calculation

In the first version of the study, the sample size has been calculated considering the context of the first COVID outbreak and taking into account that it was a unicentric study, so the following was considered:

Given that this is a unicentric study in which the experimental treatment is applied in certain phases and on specific days, and that depends on the ability to obtain donors and patients with specific characteristics, added to the context in which it is carried out, in which the number of patients hospitalized in HUSLL decreases every day, adding the factor that in the Balearic Islands the number of hospitalized has been lower, added to not having any definitive data so far that allows us to calculate the sample size safely and due to the urgency of the situation. It is required to collect the plasma sample from patients discharged from HUSLL and apply it to all those hospitalized patients who agree to participate in the study after being informed and signing the informed consent, both those hospitalized in the COVID-19 plant and in the HUSLL ICU. This is further justified if we consider the fact that currently in HUSLL there are less than 100 patients admitted for COVID-19, which is a low number, taking into account also that not everyone will want to participate. Therefore, plasma must be collected, and treatment applied to all those who sign the informed consent.

In this new version of the study (version 2.0) the context of the study changes, since it is a multicentre study, and the epidemiological framework is slightly better known. Therefore, the sample size is estimated as follows:

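### Safety and tolerance are to be compared with standard treatment, but section 5 gives a p < 0.05 rule and no between-arm estimate, confidence interval, margin or upper bound for harms

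*Combined protocol and SAP*

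**What the plan says.** Two of the secondary objectives in section 3.2.2 are comparative harm objectives: "To assess the safety of experimental reinforced treatment, comparing it with standard treatment during and after treatment" and "To assess the tolerance of experimental reinforced treatment, comparing it with standard treatment during and after treatment".

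Section 5 is the whole statistical plan and has no part specific to safety. For description it says: "With the categorical variables, the global percentages and frequencies will be estimated". For testing after the intervention it names "the student's t test of paired samples or the Wilcoxon test for quantitative variables", and repeated-measures ANOVA or Friedman for qualitative variables. It adds correlations and an unspecified multivariate analysis. Its one inferential criterion is that p < 0.05 "shall be considered an indicator of a significant difference".

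Four other places bear on the harm comparison:

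- **Section 4.3.3** lists a per-patient yes/no indicator of adverse events of grade III or above, and 15- and 30-day mortality. The cumulative adverse event rates, both any grade and grade III or above, are defined for one arm only ("GIII in experimental branch").
- **Section 4.2.9.1** sets the recording duty: "The investigator must record all non-serious and severe AAs related to the study treatment that occur", from consent to 30 days after the last dose.
- **Section 4.2.10** gives no target N for version 2.0 and seeks as many recipients as possible. Section 4.3.2 extends recruitment until the number is sufficient, without defining that, and sets 21 days of follow-up, extendable where patient safety requires it.
- **Section 4.1** describes assignment with equal probability to the two groups and also a 1:2 control-to-treated ratio.

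**The concern.** A test at p < 0.05 asks whether a difference has been shown. A safety objective asks how large an excess of harm can be excluded. In a small trial the two come apart: a real excess can easily give p > 0.05. The plan supplies no interval or margin to show what that result leaves open.

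This matters more here because the trial is a phase I pilot with no fixed size, so nothing in the design ensures that a non-significant harm test is informative. A report that follows section 5 could state that severe events or deaths did not differ significantly, and the reader could not tell whether a large excess on plasma had been ruled out.

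**Working it through.** The plan states no sample size, power or event rate for harms, so it has no figure to reproduce. What follows is an illustration under stated assumptions.

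**Inputs**

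- Significance level 0.05: section 5. Sidedness is not stated; two-sided is assumed.
- Allocation: 1:2 control to plasma (section 4.1). Because the same section also describes equal probability, 1:1 is shown as well.
- N: not in the documents. N=60 and N=99 are assumed.
- Control rate p of severe events: not in the documents. 5%, 10%, 20% and 30% are assumed.
- True effect: a doubling to 2p. This is assumed.
- Test: two-sided Fisher exact. This is also assumed, because section 5 names no between-arm test for a binary outcome.

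**Probability of missing a doubling**

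Miss = 1 − Σᵢ Σⱼ Bin(i; n_C, p) · Bin(j; n_P, 2p) · 1[Fisher p-value < 0.05]

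| N | Control / plasma | 5% vs 10% | 10% vs 20% | 20% vs 40% | 30% vs 60% |
|---|---|---|---|---|---|
| 60 | 20 / 40 | 98% | 88% | 72% | 49% |
| 99 | 33 / 66 | 93% | 81% | 51% | 23% |
| 60 | 30 / 30 | 98% | 90% | 70% | 44% |
| 99 | 50 / 49 | 90% | 75% | 44% | 15% |

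For 10% vs 20% at 1:2, the miss rate is still 69% at N=150 and 41% at N=300. By the normal approximation, 80% power for a doubling at 1:2 needs a total of 1017, 465, 189 and 96 patients for control rates of 5%, 10%, 20% and 30%.

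**What an interval would add**

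Take a hypothetical result at N=99: 13/66 severe events on plasma and 3/33 in controls.

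- Fisher p = 0.25, so under section 5 no significant difference is indicated.
- Rates: 13/66 = 0.197, Wilson limits 0.119 to 0.308; 3/33 = 0.091, Wilson limits 0.031 to 0.236.
- Risk difference: 0.197 − 0.091 = 0.106.
- Newcombe lower limit: 0.106 − √[(0.197 − 0.119)² + (0.236 − 0.091)²] = −0.058.
- Newcombe upper limit: 0.106 + √[(0.308 − 0.197)² + (0.091 − 0.031)²] = 0.232.

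The 95% interval is −5.8 to +23.2 percentage points, so an excess of 20 points is not excluded. The p-value alone does not show this.

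If the true rates are equal at 10%, the approximate half-width of the interval, 1.96·√[p(1 − p)(1/n_C + 1/n_P)], is 16 points at 20/40 and 13 points at 33/66. With no severe events among 40 plasma patients, the one-sided 95% upper limit is 1 − 0.05^(1/40) = 7.2%, and the two-sided exact limit is 1 − 0.025^(1/40) = 8.8%.

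**Whether the data would support a comparison**

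Section 3.2.2 asks for plasma against control. Section 4.3.3 defines the cumulative rates for the experimental arm only. Section 4.2.9.1 ties recording to events related to the study treatment, which controls, who receive no plasma, cannot have in the same sense. On the other side, the visit table in section 4.3.1 schedules an adverse event review for both arms, and the general definition of an adverse event in section 4.2.9.1 holds whatever the cause. The occasions for even-handed recording therefore exist, but the recording rule does not require it. For 30-day mortality, planned follow-up stops 9 days short (30 − 21).

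**The case against.** A reader might infer three stronger claims, and the documents support none of them.

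- **That this trial, at its likely size, would miss a doubling about 80% of the time.** No likely size is stated. The nearest statement, "currently in HUSLL there are less than 100 patients admitted for COVID-19", is a single-centre inpatient count behind version 1.0. Version 2.0 is multicentre with open-ended recruitment. Nor is there a severe event rate. Patients include ICU cases with SOFA above 6, so a control rate well above 10% is plausible; at N=99 and 1:2 the miss rate falls to 23% if that rate is 30%. About 80% is one cell of an assumed grid.
- **That safety is read only through p < 0.05.** Section 5 also plans a descriptive analysis of every variable, section 4.3.3 lists cumulative incidences, and section 4.2.9 provides for case-by-case assessment and expedited reporting. It is right to call p < 0.05 the only inferential rule.
- **That the plan treats non-significance as proof of safety.** It says no such thing. The risk lies in how a null result would be read when nothing else is offered.

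It can also be said that the unspecified multivariate analysis might yield an effect estimate with an interval. It might, but section 5 names no outcome, model or interval for it, and overall percentages carry neither an arm contrast nor a measure of precision.

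The strongest remaining objection is that an interval alone would lend precision to an unfair contrast if adverse events are ascertained differently in the two arms. That stands, and the fix must deal with it.

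**Conclusion.** The point holds in this form: the plan sets comparative safety and tolerance objectives but specifies no between-arm harm estimate, interval, margin or upper bound. The tests it names are paired, and its only inferential rule is p < 0.05. With no stated N, a non-significant harm result may be uninformative.

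The size can be given only conditionally. Over the assumed control rates of 5% to 30% at 1:2, a doubling of severe events is missed 98% to 49% of the time at N=60 and 93% to 23% at N=99. These figures rest on the assumed N, event rates, doubling and two-sided Fisher test. The recommendation does not depend on any one of them, since an interval shows what is excluded at whatever size the trial reaches. The plan should be changed, although no stated result or figure in it is shown to be wrong.

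**What to change.** In section 5, add a harms analysis covering adverse events of grade III or above, any adverse event, and 15- and 30-day mortality:

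1. Report the rate in each arm and the risk difference (plasma minus control) with a two-sided 95% Newcombe or Miettinen-Nurminen interval.
2. State the upper limit as the largest excess that the data do not exclude. For an arm with no events, give the exact upper limit.
3. Add a sentence such as: a p-value of 0.05 or more will not be interpreted as evidence that plasma is as safe or as well tolerated as standard treatment; safety statements will rest on the upper confidence limit.

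For the comparison to be fair:

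4. Define the cumulative adverse event rates in section 4.3.3 for both arms.
5. Amend section 4.2.9.1 so that adverse events are recorded alike in both arms, over the same window from assignment, whatever their judged relation to plasma.
6. Reconcile 30-day mortality (section 4.3.3) with the 21-day follow-up (section 4.3.2), and the 1:2 ratio with equal-probability assignment (both section 4.1).

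The cost is a few paragraphs, one more table, somewhat wider adverse event recording in controls and, if 30-day mortality is kept, a check of vital status at day 30. No extra patients are needed. The upper limits will probably be wide, so the safety conclusion will read less favourably than a statement of no significant difference.
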